Product complaints	X	X	X	X	X	X	X	X	
Concomitant therapies review	X	X	X	X	X	X	X	X	

Footnotes after last page of table.

Approved

Table 2-2. Schedule of Activities - Study Visits Through Open-label Treatment Period

	Treatment Period								
	Open-label Treatment Period (28 Weeks)								
PROCEDURE	Wk 24 (OLTP Entry Visit)	Wk 28	Wk 32	Wk 36	Wk 40	Wk 44	Wk 48	Wk 52/ EOS ^a	Notes
LABORATORY ASSESSMENTS									
Urine pregnancy test (females of childbearing potential only) ^d	X	X			X			X	
Urine drug test	X (to be performed at the discretion of the investigator)								
Chemistry	X (to be performed at the discretion of the investigator)							X	
CLINICAL OUTCOME ASSESSMENTS/PATIENT-REPORTED OUTCOMES									
Site re-assigns eDiary to subject					X				
eDiary					X (Daily)				Daily during assessment study months
Subject brings eDiary to center for use during visit or to return								X	Sites should retain eDiary at EOS visit
MPFID					X (Daily)				Daily during assessment study months
HIT-6								X	eDiary in clinic
MFIQ								X	eDiary in clinic
MIDAS								X	eDiary in clinic

Footnotes after last page of table.

Approved

Table 2-2. Schedule of Activities - Study Visits Through Open-label Treatment Period

	Treatment Period								
	Open-label Treatment Period (28 Weeks)								
PROCEDURE	Wk 24 (OLTP Entry Visit)	Wk 28	Wk 32	Wk 36	Wk 40	Wk 44	Wk48	Wk 52/ EOS ^a	Notes
STUDY TREATMENT									
Subject receives training on usage of autoinjector	X								
Self-administration of investigational product at clinic	X	X			X				
Self-administration of investigational product at home			X	X		X	X		
Study staff dispenses and/or reconciles investigational product		X			X			X	
Amgen investigational product ^e	X	X	X	X	X	X	X		Autoinjectors

Page 3 of 3

BP = blood pressure; DBTP = double-blind treatment period; eDiary = electronic diary; EOS = end of study; ET = early termination; HIT-6 = Headache Impact Test-6; HR = heart rate; **IRT = Interactive Response Technology**; MFIQ = Migraine Functional Impact Questionnaire; MIDAS = Migraine Disability Assessment; MPFID = Migraine Physical Function Impact Diary; OLTP = open-label treatment period; RR = respiratory rate

^a A subject who discontinues investigational product during the OLTP or who completes the study will perform the week 52/EOS visit assessments. Subjects who early terminate will complete the assessments approximately 28 (+3) days after the last dose of investigational product.

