^b All subjects will be enrolled via **IRT** in the OLTP to maintain the initial treatment blinding in DBTP. Subjects who received active treatment during the DBTP will remain on the same dose. Subjects who received placebo will receive either 70 mg or 140 mg in a 1:1 ratio.

^c Including pre-filled syringe in DBTP and autoinjector during OLTP.

^d Additional on-treatment local laboratory pregnancy testing may be performed at the investigator's discretion if there is suspicion that a female subject is pregnant or per local laws and regulations.

^e Study drug supply ceases at week 48.

Approved

Table 2-3. Schedule of Activities – Optional Interview-based Substudy (Selected US Sites Only)

PROCEDURE			Treatment Period							Notes
	Screening Period	Baseline Period	Double-blind Treatment Period (24 Weeks)							
	(up to 3 weeks before Baseline)	(4 weeks before Day 1)	Day 1 (post-rand)	Wk 4	Wk 8	Wk 12	Wk 16	Wk 20	Wk 24/ ET	
INTERVIEW-BASED SUBSTUDY										
Substudy informed consent			X ^a							
Substudy Eligibility Requirements			X							
Interview ^b			X ^c						X ^d	

DBTP = double-blind treatment period; ET = early termination; US = United States.

^a The Substudy subject informed consent can also be obtained at the same time as the main study informed consent during Screening instead of after randomization.

^b The first interview (Interview 1) will be conducted within the first week after randomization, the second interview (Interview 2) will be conducted within 1 week after the subject's last visit during the DBTP.

^c The entry interview will be conducted within 7 days from first investigational product dose.

^d The exit interview will be conducted in close proximity with the week 24 or early termination visits (within 7 days prior to week 24 visit or within approximately 14 days post early termination visit. If possible within 7 days post early termination will be targeted).

Approved

3. Introduction

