9.2.12 Optional Substudies

Up to 30 subjects will be asked to participate in an optional interview-based substudy. The substudy will be conducted at selected US sites and will consist of 2 qualitative interviews to be conducted during the first week after randomization (ie, substudy interview 1) and no later than a week after the subject's last visit in the DBTP (ie, substudy interview 2).

The objective of the substudy is to evaluate individual subjects' experiences related to migraine, especially as it relates to the impact on functioning during and between migraine attacks and the perceived effect of study treatment. The relationship between headache and migraine attack and the subject-level perception of treatment effect will also be explored and will help illustrate the subject perspective of treatment response.

Participation in the substudy is optional and a separate consent form will be requested for substudy inclusion. Substudy participants who discontinue study treatment early are encouraged to complete substudy interview 2.

Refer to [Appendix 8](#) for more information on the substudy.

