Regulatory agencies are showing increasing interest in understanding patients’ experiences of the risk-benefit related to new interventions being tested in clinical trials (FDA, 2017). Qualitative interviews at the start and end of clinical trials help to understand the patient experience of the treatment in the trial setting: their events, viability of proposed dosing regimen, and informal cost/benefit trade-offs.

Research Question and Objective(s) of the Qualitative Interview Substudy

The objective of this substudy is to assess the experience of treatment benefit experienced by subjects in Study 20170703, especially in terms of change in functioning during and in between migraine attacks, resulting from a preventive treatment for migraine.

Substudy Design

Qualitative interviews will be conducted with subjects who opt in to this optional substudy. Interviews will be conducted via entry interviews, conducted within **7** days of the first IP dose, and exit interviews, conducted within **7** days of the week 24 visit or within approximately **14** days of the early termination (ET) visit. **If possible, within 7 days from early termination notification will be targeted.**

Substudy Study Population or Data Resource

The population for this substudy will be comprised of adult subjects with migraine participating in the Amgen clinical trial of erenumab (Study Number 20170703) who opt

Approved

in to this optional substudy at selected sites. Subjects will be recruited throughout the study accrual period at approximately five (5) US-based sites participating in the main or parent clinical trial. An additional site participating in the parent clinical trial may be added to the substudy in order to ensure recruitment feasibility. Data sources will include the transcripts of audio-recordings of the telephone interviews. Clinical trial data and data to characterize the sample collected in the clinical trial (Study Number 20170703) will be accessed for the subjects interviewed as part of the current substudy, to characterize the sample.

Summary of Substudy Subject Eligibility Criteria

Study subjects must meet the following criteria to be considered for enrollment into the substudy:

- 1) Be randomized in Study 20170703 and have successfully received a first dose of investigational product (IP);
- 2) Have provided supplementary informed consent to participate in the substudy;

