- 3) Be willing and able to participate in two (2) telephone interviews lasting approximately one hour in duration each;
- 4) Able to read, understand, and speak English sufficiently to participate in the interviews;
- 5) Be willing and able to be audio-recorded during the interview sessions.

Meeting any of the following criterion will exclude a subject from enrollment into the substudy:

- 1) Unable to complete entry interview within **seven (7)** days from first IP dose;
- 2) Unable to complete exit interview within **seven (7)** days prior to week 24 visit or within approximately **14** days post early termination visit;
- 3) Has any clinically relevant medical or psychiatric condition that, in the opinion of the investigator and/or study coordinator, would interfere with the completion of the substudy activities. This includes but is not limited to language, speech, hearing or cognitive disorders that could impact a subject's ability participate in an interview-based discussion.

Approved

Substudy Duration and Substudy Procedures

Subjects are required to participate in two telephone interviews, lasting approximately one-hour each. Entry interviews will be conducted within **seven (7)** days from first IP dose; exit interviews will be conducted in close proximity with the week 24 or early termination visits (within **7** days prior to week 24 visit or within approximately **14** days post early termination visit. **If possible, within 7 days from early termination notification will be targeted**).

Subjects enrolled in the clinical trial 20170703 will be approached by clinic staff for recruitment and possible enrollment into this substudy.

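### For double-blind completers, Table 2-3 gives the substudy exit interview two conflicting windows, and the later one can fall after the first open-label dose

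*Protocol*

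**What the plan says.** The protocol times the exit interview in several places, all in current text.

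- **Table 2-3, footnote b:** "the second interview (Interview 2) will be conducted within 1 week after the subject's last visit during the DBTP".
- **Table 2-3, footnote d:** "within 7 days prior to week 24 visit or within approximately 14 days post early termination visit", with a 7-day target after early termination where possible.
- **Section 9.2.12:** "no later than a week after the subject's last visit in the DBTP", with a referral to Appendix 8 for more information.
- **Appendix 8, Substudy Design:** within 7 "days of the week 24 visit or within approximately" 14 days of the early termination (ET) visit. For week 24 it does not say before or after.
- **Appendix 8, second exclusion criterion:** inability to complete the interview within seven "days prior to week 24 visit or within approximately" 14 days after an ET visit. The procedures text and the later exit-interview paragraph give the same window.

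Three other parts of the protocol give these windows their meaning. Table 7-1 puts the last double-blind dose at week 20. Table 2-2 labels week 24 as the entry visit for the open-label treatment period (OLTP) and marks that visit in the row "Self-administration of investigational product at clinic". Appendix 8 says that the interview data concern change under the double-blind treatment and that subjects will be grouped by treatment arm after unblinding.

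**The concern.** Footnotes b and d belong to the same row of the same table, yet for someone who finishes the double-blind period they point to opposite sides of the week 24 visit. Whoever schedules the interview can follow one and breach the other.

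The choice matters because of what happens at week 24. A subject who goes on to the OLTP is due a first open-label injection at that visit. An interview in the following week is given by someone who knows they are now receiving erenumab. If that subject was on placebo, it also follows a first active dose. The interview's stated purpose is to learn what subjects experienced under blinded treatment, and its output is to be compared across the original arms. In so small a sample, a few late interviews could blur that comparison.

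**Working it through.** The protocol gives no figure to reproduce here. The check is to put the windows on one time scale and compare them.

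**Inputs.** SAP Table 5-2 gives target study day 169 for week 24 and 141 for week 20. In Protocol Table 2-1 the last double-blind visit for a completer is week 24. The window lengths come from the two footnotes.

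**Completers**

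- Footnote d: 169 − 7 = 162, so days 162 to 169.
- Footnote b: 169 + 7 = 176, so days 169 to 176.
- Overlap: day 169 at most.

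The ±3-day visit allowance in Section 9.1.2 does not change this, because both windows are counted from the same visit and move together. Reading the last double-blind visit as week 20 does not reconcile them either: 141 + 7 = 148, so days 141 to 148, which end 162 − 148 = 14 days before the footnote d window opens.

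**Position of the open-label dose.** Double-blind dosing ends at week 20, so the dose marked at week 24 in Table 2-2 is open-label. For a subject who enters the OLTP and is dosed on schedule, days 170 to 176 all follow that dose. For a completer who declines the OLTP, the two footnotes still conflict, but no open-label dose is involved.

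**Early terminators.** Footnote b gives 0 to 7 days after the last visit, and footnote d gives 0 to about 14 days after the ET visit. The first lies inside the second. Only the outer limit differs, and no open-label dose intervenes.

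**The remaining passages, for completers**

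| Place | Before week 24 | After week 24 |
|---|---|---|
| Table 2-3 footnote b | no | required |
| Table 2-3 footnote d | required | no |
| Section 9.2.12 | permitted | permitted, up to 7 days |
| Appendix 8, Substudy Design | permitted | permitted, up to 7 days |
| Appendix 8, exclusion 2, procedures, exit-interview text | required | no |

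The direct conflict is therefore footnote b against footnote d and most of Appendix 8. Section 9.2.12 and the Substudy Design sentence allow the later window without requiring it.

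**The case against.** The best case against raising this is that the intended rule can be recovered. Footnote d and three places in Appendix 8 agree on the 7 days before week 24, Section 9.2.12 refers to Appendix 8, and only one clause in footnote b truly disagrees. The interviewers use a standardized guide and ask about the end of the double-blind period. The substudy is optional and qualitative, and SAP Section 12 excludes its data. All of this stands, and it limits the weight of the point. It does not remove an instruction in the schedule table that contradicts the one two lines below it.

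A reader might also infer more than the documents support:

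- **That sites will diverge in which window they use.** Appendix 8 has one interview vendor contact participants, schedule the interviews and conduct them by telephone. A site-by-site split is not the mechanism, and no share of sites can be estimated.
- **That a late interview is with someone whom exclusion 2 bars.** That criterion governs enrolment into the substudy and concerns inability to meet the window. A subject who was able but was interviewed late is off-window, not ineligible.
- **That Section 9.2.12 is a second contradiction.** It sets only an upper limit, which an interview before week 24 satisfies.
- **That expectation would act mainly on former placebo subjects.** Subjects remain blinded to their original arm during the OLTP, so knowing that one is now on erenumab is common to all arms. What is particular to former placebo subjects is a first active exposure of at most 7 days.
- **That there are about 10 subjects per arm.** That would be 30 / 3 under equal allocation. The sample is one of convenience, and no per-arm numbers are planned.

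**Conclusion.** The inconsistency is real, and its severity is low. For double-blind completers, footnote b cannot be met together with footnote d and most of Appendix 8, except possibly on the visit day. Following footnote b can place the interview after known erenumab in any subject who enters the OLTP and is dosed at week 24 as scheduled. This rests on week 24 being the completer's last double-blind visit and on dosing according to Table 2-2.

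The number of interviews affected cannot be derived. It is bounded above by 30 and reduced by early termination, by subjects who decline the OLTP, and by however many interviews follow footnote d. The documents give no basis for the size or direction of any distortion between arms. A reader might infer a threat to the trial's main results, but no primary, secondary or safety analysis uses the interview data.

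**What to change.** Reconcile the text to one window:

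1. Delete the Interview 2 clause from footnote b of Table 2-3, leaving footnote d as the rule.
2. Reword Section 9.2.12 to match footnote d.
3. Give the Substudy Design sentence in Appendix 8 a direction, so that it agrees with exclusion 2, the procedures text and the exit-interview paragraph. Aligning to Appendix 8 as it stands would leave this gap open.
4. State that for completers the interview takes place before the week 24 visit and before any open-label dose. Keep the existing window after the ET visit for early terminators.

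The cost is protocol wording and a matching instruction to the vendor. No visit, subject or assessment is added, and the completer window stays 7 days long.

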3.1 Study Rationale

Preclinical models of migraine suggest that prolonged exposure to commonly used migraine-specific (ie, triptans) and nonmigraine specific (ie, opioids, nonsteroidal anti-inflammatory drugs [NSAIDs]) medication may produce long-lasting, pronociceptive neuroplastic changes in the trigeminal system including peripheral nerves, dorsal root ganglion, and nucleus caudalis (Meng et al, 2011). The reduction in pain-eliciting stimuli thresholds induced by acute medication appears to be temporally associated with increased release of calcitonin gene-related peptide (CGRP) on the circulatory system and was successfully abolished by a CGRP receptor antagonist in a triptan-induced medication overuse headache (MOH) rodent model (Meng et al, 2011; De Felice et al, 2010).

In Study 20120295, erenumab 70 mg and 140 mg subcutaneously (SC) every 4 weeks were superior to placebo in reducing monthly migraine days (MMD) from baseline to the last **study** month of the double-blind treatment period (DBTP) in subjects with chronic migraine (CM) with or without medication overuse status at baseline. In a prespecified subgroup analysis including subjects with CM with medication overuse (CM-MO subjects), both doses of erenumab achieved numerical and nominal superiority to placebo in reducing MMD (least-squares mean [LSM]: -3.1 days for both 70 mg and 140 mg versus placebo, $p < 0.001$), achieving $\geq 50\%$ reduction in MMD at month 3 (odds ratio: 2.67 and 2.51 for 70 mg and 140 mg, respectively; $p = -0.004$ and 0.007 , respectively) and acute headache medication days (AHMD) (LSM: -3.3 and -2.8 for 70 mg and 140 mg, respectively; $p < 0.001$) (Tepper et al, 2017). A subsequent post hoc subgroup analysis including CM-MO subjects who had failed 1 or more migraine preventive treatment further confirmed this observation with numerically superior reductions for both erenumab doses as compared with placebo in MMD (LSM: 2.54 and 4.44 for 70 mg and 140 mg, respectively), moderate to severe headache days (LSM: 1.81 and 3.82 for 70 mg and 140 mg, respectively) and AHMD (LSM: 2.61 and 4.26 for 70 mg and 140 mg, respectively). In addition, more subjects treated with erenumab (47% and 52% in 70 mg and 140 mg, respectively) met medication overuse-free status at the end of DBTP as compared with placebo (29%).

The safety profile of subjects included in the CM-MO stratum was consistent with that of the 12-week integrated safety analysis set for the erenumab clinical development program. Overall, at least 1 treatment emergent adverse event was reported for 46.2%,

48.7%, and 34.2% of subjects in the erenumab 70 mg, erenumab 140 mg, and placebo groups in the CM-MO stratum, respectively. Majority of treatment-emergent adverse events (TEAEs) were categorized CTCAE grade 1 or 2 with CTCAE grade 3 TEAEs only reported for 6.4%, 1.3%, and 5.3% of subjects in the erenumab 70 mg, erenumab 140 mg, and placebo groups. There were no CTCAE category 4 or deaths reported and serious adverse events (SAEs) were observed in 3.8%, 1.3%, and 1.8% of subjects in the erenumab 70 mg, erenumab 140 mg, and placebo groups, respectively.

Given the unmet medical need that MOH represents, and based on preliminary information obtained from Study 20120295, Study 20170703 is being conducted to confirm the efficacy of erenumab in a dedicated MOH population.

3.2 Background

3.2.1 Disease

In patients with migraine, frequent intake of acute pain medication can yield a paradoxical effect and contribute to increased pain severity and frequency of days with headache (May and Schulte, 2016). This phenomenon is often met with a cyclic pattern of further increase in acute pain medication intake and consequential clinical deterioration which may lead to “chronification” (May and Schulte, 2016) of headache attacks.

Metabolic, functional, and structural brain imaging studies involving subjects without migraine and subjects with CM with or without MOH have provided further evidence that the observed clinical deterioration associated with overuse of acute headache medication is possibly grounded on maladaptive neuroplasticity. Volume-based magnetic resonance imaging (MRI), stimulus-induced functional MRI, resting-state MRI, and positron emission tomography studies have reported changes in volume, connectivity, and metabolism in areas of the lateral pain system (the right supramarginal gyrus, right inferior and superior parietal cortex) and other encephalic areas associated with pain processing (ie, thalamus, insula, ventromedial prefrontal cortex) and the reward system (substantia nigra/ventral tegmentum, striatum, orbitofrontal cortex) (Lai et al, 2016; Riederer et al, 2013; Riederer et al, 2012; Ferraro et al, 2012a; Ferraro et al, 2012b; Grazi et al, 2010; Chiapparini et al, 2009; Fumal et al, 2006). These functional anatomical changes appeared to be distinctive of MOH irrespective of headache frequency and have been reported to improve upon successful treatment of MOH (Schwedt and Chong, 2017).

Longitudinal epidemiological studies have also strengthened the association between medication overuse and migraine chronification. In the American Migraine Prevalence and Prevention study, high frequency episodic migraine (EM) subjects (ie, 10 to 14 headache days/month) who reported medication overuse had a 12-month conversion to CM risk that was several fold higher than those who reported no medication overuse (Bigal et al, 2008).

In recognition of the potential to accompany and complicate primary headache disorders, the International Classification of Headache Disorders (ICHD) has recognized chronification of a primary headache that is associated with excessive and sustained overuse of acute medication as a secondary headache disorder termed MOH, a term that, in line with preclinical observations, implies a potential causative role for acute medication overuse in peripheral and central pain sensitization.

Medication overuse headache is believed to be a highly pervasive and underrecognized condition. Prevalence estimates in an adult Western population have been reported to range from 1% to 2% with majority of cases (ie, from 80% to 100%) having migraine as an underlying primary headache disorder either isolated or in association with another primary headache (Kristoffersen and Lundqvist, 2014). Known risk factors to date for the development of MOH include a diagnosis of migraine, high frequency of headache attacks, female gender, psychiatric comorbidity, pre-existing pain, and acute pain medication use (migraine-specific [triptans, ergotamines] or nonspecific [eg, NSAIDs, opioids], or combinations thereof), allodynia, lower socioeconomic status, and lifestyle-related factors (Diener et al, 2016).

Clinically, the association of medication overuse headache with CM has been linked to an increased risk of preventive treatment failure, stronger association with psychiatric comorbidities (ie, mood disorders, substance-related disorders), increased migraine-related disability, higher levels of health care utilization, and overall decreased quality of life (Diener et al, 2016; Raggi et al, 2015; Kristoffersen and Lundqvist, 2014). Economically, MOH places a high burden on society with the per-person annual costs being estimated to be approximately 10 times greater than those of tension-type headache and 3 times greater than those of migraine without MOH in Europe (Linde et al, 2012).

Recommended treatment options for MOH include early discontinuation of the overused acute medication, initiation or optimization of a preventive intervention, or a combination of both. Evidence to support efficacy of each 1 of these treatment modalities in isolation

or combined is limited by the lack of large randomized controlled trials in MOH (Chiang et al, 2016). A summary of current standard-of-care options and their evidentiary basis is presented in .

